8.1.1. Additional Details on Recording Adverse Events on the CRF

All events detailed in the table above will be recorded on the AE page(s) of the CRF. It should be noted that the CT SAE Report Form for reporting of SAE information is not the same as the AE page of the CRF. When the same data are collected, the forms must be completed in a consistent manner. AEs should be recorded using concise medical terminology and the same AE term should be used on both the CRF and the CT SAE Report Form for reporting of SAE information.

8.1.2. Eliciting Adverse Event Information

The investigator is to record on the CRF all directly observed AEs and all AEs spontaneously reported by the study patient/legally acceptable representative. In addition, each study patient/legally acceptable representative will be questioned about the occurrence of AEs in a non-leading manner.

8.1.3. Withdrawal from the Study Due to Adverse Events (see also the [Patient Withdrawal Section 6.3](#))

Withdrawal due to AEs should be distinguished from withdrawal due to other causes, according to the definition of AE noted below, and recorded on the CRF.

When a patient withdraws from the study because of an SAE, the SAE must be recorded on the CRF and reported, as appropriate, on the CT SAE Report Form, in accordance with the [Requirements](#) section above.

8.1.4. Time Period for Collecting AE/SAE Information

The time period for actively eliciting and collecting AEs and SAEs (“active collection period”) for each patient begins from the time the patient provides informed consent, which is obtained before the patient’s participation in the study (ie, before undergoing any study-related procedure and/or receiving investigational product) through and including a minimum of 36 calendar days after the last administration of the investigational product.

For patients who are screen failures, the active collection period ends when screen failure status is determined.

Any patient with VOD/SOS will be monitored for the study duration of 12 months from enrollment as described in [Section 7.4.1](#).

8.1.4.1. Reporting SAEs to Pfizer Safety

All SAEs occurring in a patient during the active collection period are reported to Pfizer Safety on the CT SAE Report Form.

SAEs occurring in a patient after the active collection period has ended are reported to Pfizer Safety if the investigator becomes aware of them; at a minimum, all SAEs that the investigator believes have at least a reasonable possibility of being related to investigational product must be reported to Pfizer Safety. Follow up by the investigator continues throughout and after the active collection period and until the event or its sequelae resolve or stabilize at a level acceptable to the investigator, and Pfizer concurs with that assessment.

If a patient starts a subsequent anticancer therapy (eg, consolidation, and/or conditioning regimen, or HSCT), SAEs occurring during the above-indicated active collection period (ie, within 36 days of last dose of GO) must still be reported to Pfizer Safety irrespective of any intervening treatment and causality.

Incidence of VOD/SOS will be reported for the entire study duration of 12 months, regardless of causality, or start of subsequent anticancer therapy (eg, consolidation and/or conditioning regimen, or HSCT). All cases of VOD/SOS must be reported as SAEs (recorded on the CRF and CT SAE Report Form).

8.1.4.2. Recording Non-serious AEs and SAEs on the CRF

During the active collection period, both non-serious AEs and SAEs are recorded on the CRF.

Follow-up by the investigator may be required until the event or its sequelae resolve or stabilize at a level acceptable to the investigator, and Pfizer concurs with that assessment.

If a patient begins a new anticancer therapy, the recording period for non-serious AEs ends at the time the new treatment is started; however, SAEs must continue to be recorded on the CRF during the above-indicated active collection period.

8.1.5. Causality Assessment

The investigator's assessment of causality must be provided for all AEs (serious and non-serious); the investigator must record the causal relationship on the CRF, and report such an assessment in accordance with the SAE reporting requirements, if applicable. An investigator's causality assessment is the determination of whether there exists a reasonable possibility that the investigational product caused or contributed to an AE; generally the facts (evidence) or arguments to suggest a causal relationship should be provided. If the investigator does not know whether or not the investigational product caused the event, then the event will be handled as "related to investigational product" for reporting purposes, as defined by the sponsor. If the investigator's causality assessment is "unknown but not related" to investigational product, this should be clearly documented on study records.

In addition, if the investigator determines that an SAE is associated with study procedures, the investigator must record this causal relationship in the source documents and CRF, and report such an assessment in the dedicated section of the CT SAE Report Form and in accordance with the SAE reporting requirements.

8.1.6. Sponsor's Reporting Requirements to Regulatory Authorities

AE reporting, including suspected unexpected serious adverse reactions, will be carried out in accordance with applicable local regulations.

8.2. Definitions

8.2.1. Adverse Events

An AE is any untoward medical occurrence in a study patient administered a product or medical device; the event need not necessarily have a causal relationship with the treatment or usage. Examples of AEs include, but are not limited to:

- Abnormal test findings;
- Clinically significant signs and symptoms;
- Changes in physical examination findings;
- Hypersensitivity;
- Drug abuse;
- Drug dependency.

Additionally, AEs may include signs and symptoms resulting from:

- Drug overdose;
- Drug withdrawal;

- Drug misuse;
- Drug interactions;
- Extravasation;
- Exposure during pregnancy (EDP);
- Exposure via breastfeeding;
- Medication error;
- Occupational exposure.

Worsening of signs and symptoms of the malignancy under study should be recorded as AEs in the appropriate section of the CRF. Disease progression assessed by measurement of malignant lesions on radiographs or other methods should not be reported as AEs.

8.2.2. Abnormal Test Findings

Abnormal objective test findings should be recorded as AEs when any of the following conditions are met:

- Test result is associated with accompanying symptoms; and/or
- Test result requires additional diagnostic testing or medical/surgical intervention; and/or
- Test result leads to a change in study dosing (outside of any protocol-specified dose adjustments) or discontinuation from the study, significant additional concomitant drug treatment, or other therapy; and/or
- Test result is considered to be an AE by the investigator or sponsor.

Merely repeating an abnormal test, in the absence of any of the above conditions, does not constitute an AE. Any abnormal test result that is determined to be an error does not require recording as an AE.

8.2.3. Serious Adverse Events

A serious adverse event is any untoward medical occurrence at any dose that:

- Results in death;
- Is life-threatening (immediate risk of death);
- Requires inpatient hospitalization or prolongation of existing hospitalization;

- Results in persistent or significant disability/incapacity (substantial disruption of the ability to conduct normal life functions);
- Results in congenital anomaly/birth defect.

Or that is considered to be:

- An important medical event.

Medical and scientific judgment is exercised in determining whether an event is an important medical event. An important medical event may not be immediately life-threatening and/or result in death or hospitalization. However, if it is determined that the event may jeopardize the patient or may require intervention to prevent one of the other AE outcomes, the important medical event should be reported as serious. Examples of such events are intensive treatment in an emergency room or at home for allergic bronchospasm; blood dyscrasias or convulsions that do not result in hospitalization; or development of drug dependency or drug abuse.

Progression of the malignancy under study (including signs and symptoms of progression) should not be reported as an SAE unless the outcome is fatal within the active collection period. Hospitalization due to signs and symptoms of disease progression should not be reported as an SAE. If the malignancy has a fatal outcome during the study or within the active collection period, then the event leading to death must be recorded as an AE on the CRF, and as an SAE with Common Terminology Criteria for Adverse Events (CTCAE) Grade 5 (see the [Severity Assessment](#) section).

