6.2. Study Period

The total study period at each cycle is comprised of following periods:

- GO Treatment: Starts with the first dose of GO (Day 1) and ends with the last dose of GO (usually Day 7).
- Post-GO Period: Starts on the day after the last dose of GO and ends on 36 days after the last dose of GO or start of subsequent anticancer therapy, including consolidation and/or conditioning regimen. This period ends with End-of-Treatment (EOT) visit.
- If the optional second cycle of GO is administered, the same GO Treatment and Post-GO Periods are repeated starting once when Cycle 1 remission status is determined. The second cycle must be started no later than 42 days after the last dose of GO. This period ends with End-of-Treatment (EOT) visit.
- Follow-up Period: Starts on the day after EOT visit and ends when a patient completes 12 months on the study or death, whichever occurs first. This is end of study for each patient.

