		Statistical details for LS means, SE, and CI were provided and was updated to include only data from Cycle 1.	Further details for the linear model were provided for clarity. Only data from Cycle 1 will be included because Cycle 2 was optional and at the investigator's discretion.
		Analyses for impact of COVID-19 pandemic were added.	Since study enrollment and conduct was ongoing during the COVID-19 pandemic, conventions and analyses were added per company guidance
		Missing PK data conventions were clarified.	The clarifications were made consistent with standards.
		References to listings were modified.	Consistent with standards changes, the focus is on listings required for an ICH CSR.
		Plots of PK parameters were removed.	The plots were to contain summaries for adult and pediatric patients, but pediatric enrollment has not completed
		Descriptive statistics summary of PK concentrations were added. Mean plots were removed.	The descriptive summary was inadvertently omitted from SAP version 1. Consistent with current reporting guidance some outputs were omitted to streamline reporting.
		Graphical summary of change in QTcF from baseline was added.	A graphical summary for the primary endpoint was added to streamline the presentation in the CSR.
		The descriptions of the immunogenicity summaries were modified.	Updates are consistent with current standard summaries.

SAP Version	Version Date	Change	Rationale
		Overall Survival: the probability of an event at 6 months was added. [REDACTED]	The probability of an event at 6 months was added to provide an estimate in the event the 12 month probability is zero. [REDACTED]
		Summaries of height, weight, and BMI were removed from Baseline Characteristics.	The summaries were removed to facilitate production of in-text CSR tables consistent recently introduced conventions for studies.
		Prior and Follow-Up HSCT definition has been clarified.	The definition was inadvertently not previously provided.
		Summary of protocol deviations was added.	This addition is consistent with the standard process.
		Clarifications of summaries including categorization of transplant relative to GO dose which had a typographical error, and the start of Cycle 2 which needed an additional category were added.	The updates were made to correct typographical errors, and details were added consistent with the CRF.

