#### **3.5.1. Adverse Events**

AEs will be graded by the investigator according to the CTCAE version 4.03 and coded using the Medical Dictionary for Regulatory Activities (MedDRA).

An adverse event is considered treatment emergent relative to a given treatment if the event starts after the first dose of study treatment. Although time will be collected on the exposure

CRF, time will not be collected on the AE CRF. Refer to Section 5.3.1, for details, but adverse events occurring on the same day as the first dose of study treatment will be considered to have occurred during the on-treatment period.

Because the protocol requires collection of VOD/SOS for the entire duration of the study, all collected AEs that start after the first dose of study treatment will be included as treatment emergent.

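### Protocol 8.2.3 gives two incompatible rules for leukemia deaths after the active collection period, so the Grade 5, SAE and fatal-AE tables depend on which sentence each site follows

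*Protocol*

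**What the plan says.** **The two rules, both in Protocol 8.2.3.** The first sentence on progression says that it "should not be reported as an SAE unless the outcome is fatal within the active collection period". The last sentence of the same paragraph opens "If the malignancy has a fatal outcome during the study or within the active collection period" and continues "then the event leading to death must be recorded as an AE on the CRF, and as an SAE", with CTCAE Grade 5.

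**The two windows.** Under Protocol 8.1.4 the active collection period runs from consent "through and including a minimum of 36 calendar days after the last administration of the investigational product". The study is longer: Protocol 3 sets 12 months from enrollment for each patient, and Protocol 6.2 says that the Follow-up Period "ends when a patient completes 12 months on the study or death, whichever occurs first".

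**Neighbouring rules.** Protocol 8.1.4.1 has SAEs after the active period reported to the sponsor's safety unit if the investigator learns of them. Protocol 8.1.4.2 ties recording of AEs and SAEs on the CRF to the active period.

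**The SAP.** SAP 3.5.1 states that "all collected AEs that start after the first dose of study treatment will be included as treatment emergent". SAP 3.5 extends the on-treatment period to the end of study follow-up. SAP 6.6.1 and 6.6.1.2 tabulate Grade 5 events, SAEs and fatal AEs.

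**The concern.** Take a patient who dies of leukemia in Month 5, having last received GO in Cycle 1. A site that follows the first sentence files no SAE for the progression. A site that follows the last sentence must enter an AE on the CRF and file a Grade 5 SAE. Both sites are complying with the protocol.

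Safety of the fractionated regimen is a secondary objective, and the study was planned to answer post-marketing requirements. There is one arm, so a fatal-AE percentage is read in absolute terms, with no concurrent control to absorb inconsistent recording. If sites differ, the overall count of fatal treatment-emergent events mixes two definitions, and the tables give no sign of it.

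**Working it through.** **Step 1. Apply each sentence to each period.**

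| Time of leukemia death | First sentence of 8.2.3 | Last sentence of 8.2.3 |
|---|---|---|
| Inside the active collection period | SAE | AE and Grade 5 SAE |
| After it, before Month 12 | Not an SAE | AE and Grade 5 SAE |

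The sentences agree in the first row and conflict in the second. Reading the phrase about the study as meaning on treatment does not help: the protocol sets study duration at 12 months, and the sentence names the study and the active period as alternatives.

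**Step 2. Look for a rule that settles it.** Section 8.1.4.1 covers late SAEs but does not say whether a late progression death is one. Section 8.1.4.2 limits CRF recording to the active period, which also conflicts with the last sentence of 8.2.3. Neither decides the case.

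**Step 3. Follow a late record into the SAP.** It starts after first dose, so SAP 3.5.1 makes it treatment emergent. The Grade 5 row of the high-level summary and the SAE tables (SAP 6.6.1), and the fatal-AE table from the safety database (SAP 6.6.1.2), have no 36-day cut-off. Each includes the record if the site made one.

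**Step 4. Size.** The plan states no figure to reproduce and no expected survival, so this step is illustrative.

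Inputs from the documents:
- 50 adults (Protocol 3 and 9.1).
- One cycle: last dose on Day 7, so the active period ends at about 7 + 36 = day 43.
- Latest permitted second cycle: Day 1 no later than 42 days after Cycle 1 Day 7, so 7 + 42 = day 49; last dose at day 55; active period ends at about 55 + 36 = day 91.
- Study end: day 365.

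Assumptions: exponential survival, median m of 3, 6, 9 or 12 months, all deaths from leukemia.

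Formulas: λ = ln 2 / (30.4375 m); S(t) = exp(−λt); expected deaths in the disputed window = 50 × [S(t₁) − S(365)], with t₁ = 43 or 91.

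Example, m = 6: λ = 0.6931/182.625 = 0.003795; S(43) = 0.849; S(365) = 0.250; 50 × (0.849 − 0.250) = 30.0.

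| Median (months) | Deaths to day 43 | Days 43 to 365 | Days 91 to 365 | All deaths to day 365 |
|---|---|---|---|---|
| 3 | 13.9 | 32.9 | 21.9 | 46.9 |
| 6 | 7.5 | 30.0 | 22.9 | 37.5 |
| 9 | 5.2 | 25.0 | 19.9 | 30.1 |
| 12 | 3.9 | 21.1 | 17.1 | 25.0 |

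The disputed window holds about 17 to 33 of 50 adults (34% to 66%). If everyone had one cycle, disputed deaths outnumber undisputed ones at every median. If everyone had the latest second cycle, deaths to day 91 (last column minus the one before it) are about 25, 15, 10 and 8, so at a 3-month median the undisputed deaths are slightly more numerous. These are upper values for each assumed median, because some deaths will have other causes.

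**The case against.** The strongest reply is that the damage is confined to a few tables and that the SAP already supplies most of what a reader needs.

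- **The death table is independent of 8.2.3.** SAP 6.6.2 tabulates all deaths, deaths within 36 days of last dose and deaths within 30 days of first dose, with cause of death, from the death CRFs. SAP 6.2.4 reports survival and cause of death. This stands.
- **Late events are partly separated.** SAP 5.2.4 ends the last cycle at 36 days after last dose or at the start of subsequent anticancer therapy, whichever is earlier. SAP 5.2.5 assigns later AEs to a Follow-up group, and SAP 6.6.1 gives treatment-emergent AEs by cycle and maximum grade. This stands in part. Assignment is by AE start date, so an event that starts in the window and becomes fatal later stays with the cycle. The split does not reach the high-level Grade 5 row, the SAE tables or the fatal-AE table, and it cannot repair differences in what sites recorded.
- **Other protocol text favours the shorter window.** Section 8.1.4.2, section 6.2.4 and footnote 16 of Table 1 all tie AE recording to about 36 days. This makes universal late recording less likely, but does not override a sentence that says such deaths must be recorded.

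Three stronger readings are tempting. A reader might infer that mortality in this study cannot be interpreted; the death table and survival analysis show otherwise. A reader might infer that nearly every patient could appear as a fatal treatment-emergent AE; that needs the shortest assumed median, every death from leukemia and every site following the last sentence, and the documents establish none of these. A reader might take the reason given in SAP Table 1 for adding a 6-month survival estimate, "to provide an estimate in the event the 12 month probability is zero", as a forecast of no survivors; it is a contingency, not an expected result.

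**Conclusion.** The contradiction is real and follows from the text alone: for a leukemia death after the active collection period and within the 12-month study, 8.2.3 both excludes and requires an SAE, and nothing else in the protocol or SAP decides between them. The outputs at risk are the overall Grade 5 row, the SAE tables, the fatal-AE disclosure table and SAE reporting itself.

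The size is uncertain. The range of 17 to 33 of 50 adults rests on assumed survival and on attributing every death to leukemia. How far the tables would be distorted also depends on how sites actually read the paragraph, which the documents cannot show. The point is worth correcting because these are the tables from which a fatal-event rate for the regimen would be quoted; it does not threaten the primary analysis.

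**What to change.** **Protocol.** Reconcile the two sentences in 8.2.3 so that both use one stated window, make 8.1.4.1 and 8.1.4.2 consistent with it, and send sites a clarification. Since 8.1.4 sets only a minimum of 36 days, the window should be written as a definite limit. Which window to adopt is for the sponsor to decide.

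**SAP.** Keep every recorded event. Present Grade 5 treatment-emergent AEs and fatal SAEs split by death within 36 days of last dose versus later, and by disease progression versus other cause, using the date and cause of death already collected. For leukemia deaths inside the active period the two sentences agree, so the early rows are comparable across sites even for data already recorded. Footnote the later rows as dependent on site practice, and refer to the death table for the complete count.

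Late fatal events already on file should not be dropped from the Grade 5 counts. SAE reports carry a causality assessment and event detail (Protocol 8.1 and 8.1.5) that a date and cause of death do not replace.

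**Cost.** A short protocol edit, a clarification letter and a few extra table rows. If the shorter window is chosen, late progression deaths will lack SAE-level causality detail. If the longer one is chosen, sites will file more SAE reports and the CRF recording period in 8.1.4.2 must be extended for these deaths.

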8.2.4. Hospitalization

Hospitalization is defined as any initial admission (even less than 24 hours) in a hospital or equivalent healthcare facility, or any prolongation of an existing admission. Admission also includes transfer within the hospital to an acute/intensive care unit (eg, from the psychiatric wing to a medical floor, medical floor to a coronary care unit, or neurological floor to a tuberculosis unit). An emergency room visit does not necessarily constitute a hospitalization; however, the event leading to the emergency room visit is assessed for medical importance.

Hospitalization does not include the following:

- Rehabilitation facilities;
- Hospice facilities;
- Respite care (eg, caregiver relief);
- Skilled nursing facilities;
- Nursing homes;
- Same-day surgeries (as outpatient/same-day/ambulatory procedures).

Hospitalization or prolongation of hospitalization in the absence of a precipitating clinical AE is not in itself an SAE. Examples include:

- Admission for treatment of a preexisting condition not associated with the development of a new AE or with a worsening of the preexisting condition (eg, for workup of a persistent pretreatment laboratory abnormality);
- Social admission (eg, patient has no place to sleep);
- Administrative admission (eg, for yearly physical examination);
- Protocol-specified admission during a study (eg, for a procedure required by the study protocol);
- Optional admission not associated with a precipitating clinical AE (eg, for elective cosmetic surgery);
- Hospitalization for observation without a medical AE;
- Preplanned treatments or surgical procedures. These should be noted in the baseline documentation for the entire protocol and/or for the individual patient;
- Admission exclusively for the administration of blood products.

Diagnostic and therapeutic noninvasive and invasive procedures, such as surgery, should not be reported as SAEs. However, the medical condition for which the procedure was performed should be reported if it meets the definition of an SAE. For example, an acute appendicitis that begins during the reporting period should be reported if the SAE requirements are met, and the resulting appendectomy should be recorded as treatment of the AE.

